9.4.3 Concomitant Medications

Prophylactic medication for the prevention of nausea and vomiting 24 hours prior to the start of radiation therapy through the full course of radiation therapy is prohibited, with the exception of the study drugs. Corticosteroids will be allowed for treatment of cerebral swelling. Rescue medication for treatment of nausea and vomiting is permitted while receiving radiation therapy at the discretion of the investigator. The date(s) of the rescue medication administration will be recorded in the patient medication log (see appendices).

9.5 Study Drug Blinding

Not applicable

9.6 Randomization

A permuted block randomization will be used to assign patients, in an unblinded fashion, to one of two treatment sequences as described in Section 9.1. A 1:1 allocation ratio will be used.

9.7 Rationale for Selection of Dose, Regimen, and Treatment Duration

Rolapitant is an FDA-approved, novel long-acting new highly selective NK_1 receptor antagonist (RA) that is designed to be given in combination with a $5HT_3$ -RA (i.e. ondansetron) to prevent CINV. Based on preclinical data and the half- life (170 hrs.) described previously and below, **one oral** rolapitant dose of 180 mg will be administered in combination with oral daily ondansetron at 8 mg/day to provided antiemetic coverage for 3 weeks of radiation (3-half-lives for rolapitant). Sequence A involves administration of ondansetron alone for 3 weeks followed by the use of rolapitant X 1 dose plus ondansetron for 3 weeks; whereas sequence B involves the use of rolapitant X 1 dose plus ondansetron for 3 weeks followed by 3 weeks of ondansetron alone. For the rolapitant plus ondansetron weeks (1 or 4), patients will self-administer the oral rolapitant pill 1-2 hours before the first fraction of radiation on the planned week (see schema). The rolapitant doses will be supplied by TerSera.

9.8 Definition of Evaluable Subjects, On Study, and End of Study

An evaluable subject is defined as a patient who meets eligibility criteria and completes at least two weeks of radiation for first CR and ~ 6 weeks of radiation for additional secondary outcomes.

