15.1 Analysis Sets

The analysis of the complete response endpoint will focus on all patients randomized to sequence A or B. However, the analysis of the patient preference endpoint will focus on those patients who have experienced both regimens and provided a preference assessment. Safety analyses will include all patients who receive protocol treatment.

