15.4 Primary Objective

The primary objective of this study is to compare the efficacy of rolapitant plus ondansetron vs. ondansetron alone in the prevention of nausea and vomiting, as measured by the overall complete response rate, among malignant glioma patients during RT and concomitant TMZ (see Section 8).

As described in Sections 15.6 and 15.7, the study was originally designed to enroll 170 glioma patients with the expectation that 160 patients would be randomized to receive one of two treatment sequences of anti-emetic therapy for the prevention of nausea and vomiting associated with RT and concomitant TMZ. A formal interim analysis was planned after 80 patients had been randomized (i.e. 40 patients to each treatment sequence). As of mid-January 2022, 53 patients had been randomized. On January 18, 2022, TerSera, the study's funding source, requested that accrual to the study be terminated in the next few months.

Given this request from TerSera, the accrual target for this study is reduced to 57 patients. The decision to terminate early has not been influenced by the data collected to date, as no interim analyses have been conducted. The analyses as described below will be conducted; however, they may no longer have the power to detect the hypothesized effect size.

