15.4.1 Variable

Complete response (CR) rate associated with rolapitant plus ondansetron and that associated with ondansetron during the first two weeks of RT and concomitant TMZ is defined as the proportion of patients with no emetic episode or use of rescue medication while receiving radiation and concomitant TMZ. The CR rate will be assessed via the modified MASCC Antiemesis Tool (MAT).¹⁷

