15.4.2 Statistical Hypothesis, Model, and Method of Analysis

As the primary analysis, a chi-square test will compare treatment regimens (ondansetron alone vs rolapitant + ondansetron) with respect to the proportion of patients who experience a CR during the first 2 weeks of RT and TMZ treatment. As an additional analysis, logistic regression will assess the effect of potential confounders on this relationship. Among the covariates that will be considered is the dose of decadron administered during the 2 weeks of RT and TMZ treatment.

As an exploratory analysis, a generalized linear model with a logit link that accounts for correlation between the CR status observed during the first and second treatment period within the same patient will be used to assess the impact of period, treatment, and their interaction. The purpose of this latter analysis is to assess whether the incremental effect of combination treatment relative to ondansetron alone is the same whether rolapitant is administered during the first period (i.e. first 3 weeks) or the second period (i.e. the second 3-week treatment regimen). It should be noted that this test will have low power to detect a clinically meaningful interaction effect. Within the context of the generalized linear model described above, the impact of covariates on CR rate will be explored. Included among these covariates will be the dose of decadron administer during that segment of the treatment regimen.

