One hundred sixty (160) patients will be randomized to either sequence A or B with the expectation that 152 patients will provide an assessment of their experience during the first 2 weeks of treatment with the first regimen. With 152 patients, there is 80% power to detect an increase in the CR rate from 75% with ondansetron to 90% with the combination of ondansetron and rolapitant (α =0.05; one-tailed).

Power Calculations for Patient Preference, KEY Secondary Endpoint: The hypothesis of this study is that patients will prefer the combination of ondansetron and rolapitant over ondansetron alone for the prevention of nausea and vomiting. If no overall preference exists, then the percentage of patients who choose combination treatment is expected to be approximately 50%. The hypothesis that will be tested is whether the proportion of patients who prefer combination treatment is greater than 50%. Statistically, the hypothesis that will be tested is:

H0: $p \le 0.5$ vs H1: p > 0.5

where p is the proportion of patients who prefer combination treatment over ondansetron alone. Under the assumption that approximately 140 patients will have experienced both regimens and provided a preference assessment, the study has 93% power to detect a preference rate of 65% or greater with a two-tailed test conducted at the 0.05 level of significance.

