15.7.2 Modified Study Design

As described in Section 15.4, the sample size goal for this study is reduced to 57 patients. With 57 patients, there is 80% power to detect an increase in the CR rate from 75% with ondansetron to 97% with the combination of ondansetron and rolapitant (α =0.05; one-tailed). Alternatively, there is 80% power to detect an increase in CR rate from 63% to 90%.

Relative to patient preference, with 57 patients, the study has 83% power to detect a preference rate of 69% or greater with a two-tailed test conducted at the 0.05 level of significance.

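### Section 9.8 makes completing two weeks of radiation a condition of evaluability for CR, Section 15.1 analyses everyone randomised, and no rule connects the two or scores incomplete patients

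*Combined protocol and SAP*

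**What the plan says.** - **Section 9.8** ties evaluability for the primary endpoint to eligibility and to finishing part of radiotherapy: "An evaluable subject is defined as a patient who meets eligibility criteria and completes at least two weeks of radiation for first CR".
- **Section 15.1** sets no such condition: "The analysis of the complete response endpoint will focus on all patients randomized to sequence A or B". Its next sentence narrows the population for the preference endpoint only.
- **Section 15.4.1** defines the CR rate as "the proportion of patients with no emetic episode or use of rescue medication while receiving radiation and concomitant TMZ", over the first two weeks. It gives no rule for incomplete follow-up.
- **Section 15.4.2** says that "a chi-square test will compare treatment regimens" but names no population.
- **Section 15.7.1** plans 160 randomised and expects that "152 patients will provide an assessment of their experience during the first 2 weeks". The original power rests on those 152.
- **Sections 15.4 and 15.7.2:** "the accrual target for this study is reduced to 57 patients", and "With 57 patients, there is 80% power to detect an increase in the CR rate from 75% with ondansetron to 97% with the combination" (one-sided 0.05). A second 80% statement covers 63% versus 90%. Neither allows for patients without an outcome.
- **Sections 9.5, 9.6 and 12.6:** assignment is unblinded. The investigator may withdraw patients, among other reasons for intolerable symptoms or non-compliance. Follow-up after withdrawal is described only for toxicity withdrawals, and withdrawn patients are not replaced.

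**The concern.** Finishing two weeks of radiation happens after randomisation. A patient who vomits on day 3 and stops radiation on day 8 is a failure under 15.4.1, yet is not evaluable for CR under 9.8. If 9.8 were applied, that known failure would leave the primary comparison. Staff who decide on withdrawal or judge eligibility know the regimen.

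Preferring 15.1 does not close the gap. Including every randomised patient requires a score for someone who stops early without an event, withdraws, or returns incomplete diaries, and none is given. Leaving such patients out recreates an assessed-only set, and the only CR-specific text to lean on is 9.8. With 57 patients, the handling of a few cases can matter to the primary conclusion.

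**Working it through.** **1. The plan's own power.** Inputs from 9.6, 15.7.1 and 15.7.2: 1:1 allocation, one-sided 0.05, n = 57/2 = 28.5 per arm. The formula is power = Φ{[Δ − 1.645·√(2p̄(1−p̄)/n)] / √([p₁(1−p₁)+p₀(1−p₀)]/n)}.

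For 75% versus 97%: Δ = 0.22 and p̄ = 0.86; the standard errors are 0.0919 (null) and 0.0872 (alternative). (0.22 − 1.645×0.0919)/0.0872 = 0.789, so power is 78.5%.

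| Scenario | Approximation | Exact enumeration of the same test |
|---|---|---|
| N=57, 75% vs 97% | 78.5% | 83.9-85.5% |
| N=57, 63% vs 90% | 78.8% | 80.3-81.7% |
| N=152, 75% vs 90% | 78.9% | 80.4% |

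The ranges reflect which arm has 29 patients. The stated 80% reproduces when every patient counted has an outcome.

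**2. How many patients might be affected.** The only figure in the documents is 8/160 = 5% without a two-week assessment. Applied to 57: 57×0.05 = 2.85, about three. This is borrowed: a missing assessment is not the same as stopping radiation, for which no rate is given.

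**3. What three exclusions can do.** z = (p₁−p₀)/√[p̄(1−p̄)(1/n₁+1/n₀)], one-sided. Those excluded are non-responders in the all-randomised table.

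| Failures dropped | All randomised, ondansetron vs combination | p | After exclusion | p |
|---|---|---|---|---|
| 1 ondansetron, 2 combination | 21/28 vs 26/29 | 0.073 | 21/27 vs 26/27 | 0.021 |
| 3 ondansetron | 20/29 vs 25/28 | 0.030 | 20/26 vs 25/28 | 0.112 |
| 2 ondansetron, 1 combination | 21/28 vs 26/29 | 0.073 | 21/26 vs 26/28 | 0.093 |

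First row: (0.8966−0.75)/0.1008 = 1.454 becomes (0.9630−0.7778)/0.0914 = 2.026. The third row starts from the same data, and the conclusion does not change.

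Across all tables with 28 combination and 29 ondansetron patients and observed CR among those kept of at least 80% and 60%, the conclusion changes in:
- 1 of 66 tables when one combination and two ondansetron patients are lost;
- 10 of 72 when two combination and one ondansetron patient are lost;
- 17 of 72 when all three are combination;
- 14 of 66 when all three are ondansetron.

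These tables are not equally likely.

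**4. Failures dropped at a common rate d.** The CR rate among those kept is p/[1−(1−p)d]. With d = 10% (assumed), 0.75/0.975 = 76.9% and 0.90/0.99 = 90.9%, so a 15-point difference becomes 14.0. By simulation (75% versus 90%, 57 patients), the two sets disagree in about 4% of trials at d = 4% and 8-9% at d = 10%, more often to rolapitant's disadvantage. With 75% in both arms, the rejection rate stays near 5%.

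**5. Loss unrelated to outcome.** If 5% per arm are not evaluable at random and are scored as non-CR in the all-randomised set, the two sets disagree in 15% of simulated trials (75% vs 90%), 19% (75% vs 97%) and 3% (no effect).

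**6. Power if 5% are scored as failures.** 0.95×0.75 = 0.7125 and 0.95×0.97 = 0.9215. Exact power at 57 is 68.2-69.1%, against 83.9-85.5% with no loss by the same method.

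**The case against.** The strongest reply is that 15.1 already answers the question. It is the analysis-set section and names all randomised patients for CR. It then restricts preference alone, and nothing in Section 15 uses the 9.8 definition. That stands. A reader might infer that the plan offers two equally valid primary populations. It does not: a primary analysis confined to the 9.8 set would depart from 15.1. Nor are the 152 a third analysis set; they are an attrition expectation.

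It is also fair that 9.8 depends on stopping standard radiotherapy, not on stopping an antiemetic or a diary. Rescue is allowed in both arms, and Section 9.2 cites grade 3/4 nausea and vomiting below 1% with a 5HT₃ antagonist. Nothing in the documents supports a large share of failures abandoning radiation within two weeks. The changes of conclusion in step 3 are selected splits; where losses follow failures, ondansetron should lose more, and a split of two to one in that direction seldom changes the conclusion.

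What the reply leaves untouched is that 9.8 remains a written, unreconciled rule for CR, and that 15.1 cannot be carried out for incomplete patients without a scoring rule.

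**Conclusion.** The point holds as an unreconciled definition together with a missing scoring rule on the primary endpoint. About three patients of 57 can move the one-sided p-value across 0.05, in either direction. Whether they would depends on their number, their split by arm and how they are scored, none of which the documents give; the 4%, 5% and 10% rates are assumptions.

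Two stronger readings are not supported. One is that 9.8 would manufacture a win for rolapitant: with failures dropped at a common rate, the usual effect is a smaller difference and less power, and a spurious gain needs losses that differ by arm. The other is that the stated 80% is wrong: it reproduces when all 57 contribute an outcome, and Section 15.4 already warns of reduced power. The 68-69% figure follows only if unassessed patients are counted as failures and 5% are unassessed.

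**What to change.** 1. State in 9.8 and 15.1 that the primary CR analysis includes all randomised patients, whatever a later eligibility review finds and whether or not radiation was completed.
2. Count any emesis or rescue recorded on days 1-14 before stopping as a failure.
3. Prespecify one rule for event-free patients with incomplete data: for example, failure in the primary analysis with complete-case as sensitivity, or the reverse. Both analyses should be reported, because scoring as failure is not always conservative. With no true effect (75% in both arms) and 10% lost on ondansetron only, it rejected in about 15% of simulated trials.
4. Use the 9.8 set only for description or sensitivity.
5. Note in 15.7.2 that the 80% assumes 57 outcomes, and restate it if the chosen rule scores unassessed patients as failures.

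The cost is a wording amendment, made before outcomes are analysed, and possibly a less favourable power statement. No new data are needed.

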9.9 Early Study Termination

This study can be terminated at any time for any reason by the PI-sponsor. If this occurs, all subjects on study should be notified as soon as possible. Additional procedures and/or follow up should occur in accordance with Section 12.6, which describes procedures and process for prematurely withdrawn patients.

10 STUDY DRUG

10.1 Names, Classification, and Mechanism of Action

Rolapitant or Varubi® (formerly referred to as SCH 619734) is an FDA-approved potent, selective, competitive neurokinin-1 (NK₁) receptor antagonist with no known activity at other pharmacologic targets. It binds with high affinity to the human NK₁ receptor (Ki = 0.66 nM) and competitively antagonizes functional effects mediated by activation of the NK₁ receptor in cultured cells (Kb = 0.45 nM). The endogenous activator of NK₁ receptors is the neuropeptide Substance P. Rolapitant does not have significant affinity for NK₂ or NK₃ receptors or for a battery of other receptors, transporters, enzymes, and ion channels. The compound is active in animal models of chemotherapy-induced nausea and vomiting (CINV) and has demonstrated efficacy in phase 2 studies in patients receiving highly emetogenic chemotherapy (HEC). Because NK₁ RA is known to be effective in CINV have also been shown to be effective in postoperative nausea and vomiting (PONV), rolapitant has also been investigated and shown to be effective in a phase 2 study in the prevention of PONV.

The first indication for which rolapitant is being developed is the prevention of CINV. CINV has both an acute (0 to 24 hrs.) and delayed (>24 to 120 hrs.) phase and it was expected that rolapitant will be very effective in preventing CINV both phases in patients receiving either HEC or MEC agents. Cisplatin doses \geq 60 mg/m² represent the standard chemotherapy agent used in many clinical trials to determine effectiveness of anti-CINV therapies against a HEC regimen. MEC includes chemotherapy agents that are categorized as Hesketh 3 or 4 and include carboplatin, cisplatin (<50 mg/m²) and cyclophosphamide regimens such as cyclophosphamide 750 – 1500 mg/m² IV alone or combined with other chemotherapy agents and

cyclophosphamide 500 – 750mg/m² administered with other emetogenic chemotherapy (Hesketh level 3, other than cyclophosphamide). MEC clinical trials often include breast cancer patients receiving a combination of intravenous cyclophosphamide plus an anthracycline drug such as doxorubicin or epirubicin. There are both acute (0 to 24 hrs.) and delayed (>24 to 120 hrs.) phases of CINV which are distinct after HEC but less differentiated after MEC.

10.2 Packaging and Labeling

The drug product will be supplied in blister packs containing two (2) 90 mg tablets provided by TerSera.

10.3 Supply, Receipt, and Storage

Study drug supplies must be stored in a secure, limited-access location under the storage conditions specified on the drug supply label. Rolapitant tablets are stored at controlled Room temperature, 20-25°C (68-77°F); excursions permitted to 15-30°C (59-86°F).

10.4 Dispensing and Preparation

There is no preparation as each 90 mg pill is packaged in a separate sealed blister pack. The study pharmacist will dispense 2-90 mg pills (for a total dose of 180mg) to the patients to be administered either on week 1 or 4 depending on assigned sequence as directed by the study team.

10.5 Compliance and Accountability

Patients will be reminded by the study team to begin rolapitant during week 1 or 4 of radiation depending on assigned sequence. Patients will also be reminded to take daily ondansetron. Compliance will be recorded by study coordinator through weekly patient questioning and patient recording in medication log (see appendices). Of note compliance is a secondary objective (see Section 15.5).

10.6 Disposal and Destruction

The ICS will either destroy or return the unused study drug at the discretion of TerSera. The investigational pharmacist will be responsible for performing and documenting such activities.

10.7 Other Study Drugs (Ondansetron)

10.7.1 Description

Ondansetron is a first generation 5-HT₃-RA (serotonin-3).

10.7.2 Source

Ondansetron (Zofran) is commercially available and will not be provided in this study.

10.7.3 Dosage and Administration

Ondansetron will be administered on both arms of the protocol at 8 mg p.o, daily on Days 1- 42 days, 30-60 minutes prior to each dose of chemotherapy. A prescription for Ondansetron 8 mg p.o. daily 30-60 minutes before temozolomide X 7 days (with 6 refills) will be provided by provider.

10.7.4 Drug Ordering

Ondansetron is commercially available and will not be provided in this study. A prescription for Ondansetron will be given to the patient on both arms of the study.

11 SUBJECT ELIGIBILITY

11.1 Inclusion Criteria

Selection of Subjects: Patients with a malignant glioma who plan to undergo standard RT with concomitant daily temozolomide (TMZ) therapy.

Please refer to section 5.4 for a complete listing of the Inclusion Criteria.

11.2 Exclusion Criteria

Please refer to section 5.4 for a complete listing of the Exclusion Criteria.

12 SCREENING AND ON-STUDY TESTS AND PROCEDURES

Patients will be initially screened during the -28 to 0 days prior to study initiation. During this time period, the following will be recorded: physical examination; vital signs and weight; laboratory studies (complete blood count with differential, platelet, blood chemistries, liver function tests and urinalysis); past medical history; concomitant medications (steroids and anticonvulsants); and predictors of RINV (e.g. irradiation site, planned dose, treatment field, alcohol intake, gender, age). Prior to study enrollment, patient's medications should be reviewed by the clinical pharmacist to prevent concerns with drug interactions. The patient's medications will be evaluated by the PI, the patient's study physician, and/or the study pharmacist on a case by case basis for safety. Laboratory evaluations, performance status, concomitant medications, and adverse events for final eligibility should be confirmed within 2 weeks of initiating radiation with concomitant TMZ.

Patients will be filling out data collection tools (i.e. MAT and TSMQ-9) day 0 (baseline) and days 1, 2, 4, and 7 (for days 7, 1, 2-3, and 4-6, respectively) of each week of radiation therapy. In addition, they will be recording their medication and the use of rescue medication in a medication log as noted below (See Section 12.7 and appendices for study tools).

The CRC will be collecting data from the tools listed below and placing data in an electronic database that is 21CFR Part 11 compliant (e.g. Medidata Rave). Monthly meetings between the CRC and primary investigators will occur to review data. Patient Surveys and follow up phone calls will be conducted weekly to obtain and validate data. The CRC is required to monitor protocol patients weekly or as many times as necessary to obtain toxicities. Toxicities are obtained via clinical notes or telephone conversations with the local oncology office and/or patient. The National Cancer Institute (NCI) Common Toxicity Criteria (CTC) Version 4 is to be used to score the adverse advents. All graded toxicities are then entered in the database and reviewed together with the Primary Investigator (PI) and CRC and confirmed by source documents. Attributions are approved by primary investigators.

Table 7: Screening and Study-related Tests and Procedures

| Phase | Screen | Start | Study Period | | | End | |
|---|----------------|-------|-------------------------|-------|--------------------|-------|--------------------|
| Week of radiation | -4 to 0 | 1 | 2 | 3 | 4 | 5 | 6 |
| Days of radiation | -28 to 0 | 1-7 | 8- 14 | 15-21 | 22-28 | 29-35 | 36-42 |
| General Evaluations | | | | | | | |
| Informed Consent | Х | | | | | | |
| Eligibility Criteria | X ⁵ | | | | | | |
| Past Medical History | | | | | | | |
| (RINV predictors) | Х | | | | | | |
| Physical Exam | Х | | | | | | |
| Height, Weight, BSA | Х | | | | | | |
| Vital Signs | Х | | | | | | |
| Performance Status | X ² | | | | | | |
| Concomitant Medications | X ² | Х | | | | | |
| Adverse Events | X ² | | Continuous ¹ | | | | |
| Laboratory Evaluations | | | | | | | |
| CBC with Platelets | X ² | | | | | | |
| Serum Chemistry tests | X ² | | | | | | |
| Liver Function tests | X ² | | | | | | |
| Serum Pregnancy Test | X ² | | | | | | |
| Urinalysis | X ² | | | | | | |
| Treatment | | | | | | | |
| Sequence A: Rolapitant (Day) | | | | | X(22) | | |
| Sequence B: Rolapitant (Day) | | X(1) | | | | | |
| Sequence A/B: Daily Ondansetron | | X(1- | X (8- | X(15- | X(22-28) | X(29- | X(36- |
| | | 7) | 14) | 21) | | 35) | 42) |
| Concomitant Temozolomide | | Х | Х | Х | Х | Х | Х |
| Surveys/Medication log | | | | | | | |
| Medication Log | | Х | Х | Х | Х | Х | Х |
| MAT Survey (Day 0 (baseline) and Days 1,2,4,7/week) ³ | Х | Х | Х | Х | Х | Х | Х |
| TSQM9 Sequence A for wks1-3; 4-6 | | | | | X(22)4 | | X(43)4 |
| TSQM9 Sequence B for wks1-3; 4-6 | | | | | X(22) ⁴ | | X(43) ⁴ |

^{1.} Adverse events will be monitored until at least 30 days after the dose of Rolapitant (or 2 weeks after the end of radiation)

